## 14.4 Study Populations

The primary population for an analysis of the proof of mechanism is the Full Analysis Set (FAS)

CONFIDENTIAL Page 59 of 75

Fibrocell Technologies RDEB Phase I/II Protocol Final Version 8.0, 29 Oct 2019

population. Study populations are defined in the following sections.

#### 14.4.1 Safety Population

This population is defined as all subjects who were administered FCX-007.

#### 14.4.2 Full Analysis Set Population

TheFull Analysis Set (FAS) population includes subjects who were administered FCX-007 who have had at least one paired assessment of the target wound area post-administration.

#### 14.4.3 Per-Protocol Population

The per-protocol (PP) population is defined as all subjects in the FAS population who have had at least one paired assessment of the target wound area post-administration, and completed the protocol as planned.

### 14.5 Demographic and Baseline Characteristics

The descriptive summaries of subjects' demographic and baseline characteristics will be presented by treatment group for the safety, FAS, and PP populations. A detailed description of subject disposition will be provided.

Subject characteristics will include a summary of the following:

- Subject demographics.
- Baseline disease characteristics as determined at screening.
- Pre-existing medical conditions.

Continuous variables will be summarized using number of observations, mean and standard deviation, median and minimum and maximum values. Categorical values will be summarized using number of observations and percentages.

## 14.6 Proof of Mechanism Analyses

#### 14.6.1 Expression of Collagen VII

Biopsies collected for the purpose of IF will be evaluated for expression of C7. Each biopsy will be scored by a qualified reader. Scores will be evaluated and C7 will be considered to be expressed if an increase from baseline is observed.

Change in score from baseline will be evaluated and reported for each post-treatment visit and treatment endpoint by treatment and study phase and will be compared between treatments for each study phase. These analyses will be performed for both FAS and PP populations.

CONFIDENTIAL Page 60 of 75

RDEB Phase I/II Protocol

Final Version 8.0, 29 Oct 2019

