### 2.2.2 Secondary

- 1) To evaluate mechanism of action of FCX-007 at visits 5 (Week 4), 6 (Week 12), 8 (Week 25), 10 (Week 52), and unscheduled visits through the evaluation of skin biopsies for C7 expression and the presence of anchoring fibrils.
- 2) To evaluate the efficacy of FCX-007 through an intra-subject paired analysis of target wound area at visits 5 (Week 4), 6 (Week 12), 8 (Week 25), 10 (Week 52), and unscheduled visits, comparing FCX-007 treated wounds to untreated wounds through investigator assessment of wound healing based on the digital images of wounds.

[figure not shown]
CONFIDENTIAL Page 16 of 75

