#### 10.2 Evaluation

#### 10.2.1 Immunofluorescence (IF)

Expression of C7 is analyzed at Visits 3 (Day 0), 5 (Week 4), 6 (Week 12), 8 (Week 25) and 10 (Week 52). Skin biopsies may also be obtained at unscheduled visits to evaluate C7 per investigator discretion. A qualified reader will evaluate production of C7.

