#### 10.2.2 Immunoelectron Microscopy (IEM)

Expression of C7, both NC1 and NC2 epitopes, and the formation of anchoring fibrils are analyzed through IEM at Visits 3 (Day 0), 8 (Week 25), and 10 (Week 52). Skin biopsies may also be obtained at unscheduled visits. A qualified reader will score the presence of anchoring fibrils. as + (presence of mature anchoring fibrils) or – (absence of mature anchoring fibrils).

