#### 11.1.2.1 Criteria for the Evidence of Benefit

Evidence of benefit is defined as having any one or more of the following three criteria in a single FCX-007 treated wound:

- An increased presence of C7, defined as an increase of 1 or more, relative to baseline, on a biopsy evaluated by immunofluorescence (IF), as measured by a qualified reader.
- The presence of mature anchoring fibrils as designated by a qualified reader.
- Increase in wound healing based on investigator assessment relative to baseline (Day 0) in any wound administered FCX-007.

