#### 14.6.2 Immunoelectron Microscopy / Production of Anchoring Fibrils

Biopsies collected for the purpose of IEM will be evaluated for the presence of anchoring fibrils, LH24 and mAb185 antibody staining and C7 expression. Evaluation of each item from each biopsy will be scored by a qualified reader. LH24 and mAb185 antibody staining and anchoring fibrils will be evaluated and considered to be present if a score of + is observed.

The percent of target wounds with a + score for each item evaluated will be reported at each post-treatment visit by treatment for each study phase. For quantitative analysis, the obtained results will be assigned a numeric value of 0 and 1, respectively, for – and +. Change in score from baseline will be evaluated and reported for each post-treatment visit by treatment and study phase and compared between treatments for each study phase. These analyses will be performed for both FAS and PP populations.

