#### **Collection Procedure**

Biopsies for the purpose of manufacturing are to be obtained from normal or unaffected skin with the specific location varying on a case-by-case basis according to the judgment of the Investigator. The neck, head (with the exception of post-auricular), groin, hands, feet and axilla are excluded areas. Based on previous experience with collecting biopsies from RDEB subjects under IRB approved protocol for product development purposes, the anatomical locations including upper leg, calf, trunk and upper arms (in descending order of frequency) are recommended areas.

- Anesthetize the area by topical anesthetic, local perfusion.
- Prepare the area.
- Excise a sample of tissue using the appropriate supplied biopsy punch. The use of forceps and a scalpel may be necessary to remove the biopsy from its base.
- Gently place excised tissue into cryovial using forceps.
- Close donor site as appropriate.
- Complete associated biopsy inventory form with appropriate subject information.
- Package and ship biopsy as described in the Study Procedures Manual.

CONFIDENTIAL Page 74 of 75

Fibrocell Technologies RDEB Phase I/II Protocol Final Version 8.0, 29 Oct 2019

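### The protocol has no provision keeping the IF and IEM reader from knowing visit, biopsy location or treatment, so secondary objective 1 is open to expectation bias

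*Combined protocol and SAP*

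**What the plan says.** Section 2.2.2 sets the first secondary objective as a study of mechanism at Weeks 4, 12, 25 and 52 and at unscheduled visits, "through the evaluation of skin biopsies for C7 expression and the presence of anchoring fibrils".

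The reading itself is described in four places:

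- Section 10.2.1, on IF: "A qualified reader will evaluate production of C7".
- Section 10.2.2, on IEM: "A qualified reader will score the presence of anchoring fibrils", recorded as plus or minus.
- Section 14.6.1, on the IF analysis: "Each biopsy will be scored by a qualified reader", and "C7 will be considered to be expressed if an increase from baseline is observed".
- Section 14.6.2, on the IEM analysis: "Evaluation of each item from each biopsy will be scored by a qualified reader", with minus and plus then coded 0 and 1.

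Both analysis sections report the change in score from baseline at each post-treatment visit and compare it between treatments within each study phase. Section 14.2 calls the statistical analyses exploratory, with two-sided tests at 0.05. Section 3.1 leaves the control wound of each pair untreated.

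**The concern.** Both scores are human judgments. The IF result is relative by construction, because C7 counts as expressed when the later score exceeds the earlier one, and the current text defines no IF scale to anchor it. The IEM result is a yes-or-no call. If the reader knows that a specimen is from Day 0, or from an injected location after treatment, the hoped-for direction is known before the slide is read. Borderline material can then drift towards absent before treatment and present after it.

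No analysis can remove such a drift later, because it sits in the data. With up to 12 subjects (a seventh in Phase II is possible) and results reported by phase, a few borderline calls can alter the account of mechanism. The issue concerns a laboratory reader and laboratory specimens. It is separate from the investigator's rating of wound photographs in Section 9.3.1.

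**Working it through.** The plan gives no sample-size, power or reader-error figure to reproduce, so the main check is a comparison of the text.

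**Step 1. What each place provides.**

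| Place | What is scored | Masking, coding, reading order or second reader |
|---|---|---|
| 10.2.1 | C7 by IF | none stated |
| 10.2.2 | anchoring fibrils by IEM, plus or minus | none stated |
| 14.6.1 | IF score, change from baseline | none stated |
| 14.6.2 | IEM items, 0 or 1, change from baseline | none stated |
| 11.1.2.1 | IF increase of 1 or more; fibrils present | none stated |
| 10.1.2 | biopsy location and purpose, kept in source records | no coding step |
| Appendix B | collection, inventory form, shipping | no coding step |

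Calling the reader qualified speaks to competence. It says nothing about what the reader knows.

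**Step 2. Could the design supply masking by itself?** No. The current control is an untreated wound, with no vehicle or sham. The order of visits is fixed, so specimens read as they arrive come in time order, with Day 0 first.

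**Step 3. Does reader bias reach the analysis?** Yes. The same scores feed the change from baseline and the between-treatment comparison in both analysis sections.

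**Step 4. Direction only, under assumptions.** The plan names no test. Take an exact two-sided sign test with n discordant pairs and no true effect, where the reader favours the later or treated specimen in a share q of pairs. Both n and q are assumed. For n = 6 all six must agree, so the rejection probability is q^6 + (1 − q)^6:

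- q = 0.5 (no lean): 2 × 0.5^6 = 0.031
- q = 0.6: 0.0467 + 0.0041 = 0.051
- q = 0.7: 0.1176 + 0.0007 = 0.118
- q = 0.8: 0.2621 + 0.0001 = 0.262

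For n = 12 (rejection at 10 or more in one direction) the values are 0.039, 0.086, 0.253 and 0.558. That n would need pooling across phases or several pairs per subject. With five or fewer discordant pairs the test cannot reject, since 2 × 0.5^5 = 0.0625; a lean would then show only in the descriptive results. This shows how a lean passes into a comparison. It does not estimate how large the lean is.

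**The case against.** **The evidence is silence.** A reader might infer that the biopsies will be read unmasked. The documents do not say so. They say nothing either way, and Appendix B leaves packaging and shipping to a Study Procedures Manual that is not part of these documents and could contain a coding step. This stands, and it limits the point to a missing provision.

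**The inventory form proves little.** Appendix B says "Complete associated biopsy inventory form with appropriate subject information". A reader might infer that specimens reach the laboratory reader with an identifying form. The text does not say that the form goes to the reader or that it shows visit, location or treatment. The inference is not supported.

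**The pediatric decision.** Section 11.1.2.1 counts as evidence of benefit "The presence of mature anchoring fibrils as designated by a qualified reader", and Section 11.1.2 has the DSMB consider such evidence before children enrol. A reader might conclude that biased reads would drive that step. The schedule does not support this. The review covers data through Week 4, the criteria apply to a treated wound, and Table 2 schedules wound IF and IEM only from Week 12. The wound biopsy itemised in Section 10.1 for Week 4 is for DNA and mRNA. Only discretionary or unscheduled biopsies could supply a treated-wound read in time, and FDA approval is also required.

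**A large false-positive figure.** One could assume that 5% to 20% of negative specimens are called positive and compute 1 − (1 − p)^k, which gives 26% to 93% for at least one false call in 6 to 12 reads. That does not measure the effect of masking. A masked reader also makes errors, only the difference matters, and the documents give neither rate.

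**The consequence is limited.** The primary objective is safety, the analyses are exploratory, and the DNA and mRNA results of Section 10.2.3 depend less on a reader. All true, although Section 14.6 plans no analysis of DNA or mRNA. It is also unclear which untreated tissue supports the between-treatment comparison, so masking to visit may matter more than masking to treatment. None of this supplies masking.

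**Conclusion.** The point holds as a gap in the protocol. No provision keeps the IF and IEM reader from knowing visit, biopsy location or treatment, and secondary objective 1 rests on that reader's change-from-baseline and plus or minus scores. The exploratory comparisons in Sections 14.6.1 and 14.6.2 are therefore open to expectation bias that could readily be avoided.

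Its size cannot be derived from the documents, and the sign-test values are conditional illustrations. The conclusion assumes that no procedures manual or laboratory document already requires coded reading; if one does, a sentence in the protocol saying so closes most of the point. The case rests on secondary objective 1 alone. It is worth correcting because the correction is cheap, but it does not undermine the trial's primary purpose.

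**What to change.** - **Section 10.2 and Appendix B:** label each IF and IEM specimen with a random code only. The investigative site holds the key linking the code to subject, visit, biopsy location and treatment. Require that sections or micrographs be kept, which neither place now mentions.
- **Sections 14.6.1 and 14.6.2:** state that the analysed scores come from the existing reader scoring each subject's coded sections or micrographs together, Day 0 included, in random order and without the key. Link scores to the key only once they are final.
- **Real-time reads:** keep them for safety (DIF) and for the DSMB, and state that they are not the source of the analysed mechanism scores.

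The cost is coded labels, a key log and one batch read. No extra biopsy, visit, subject or staff member is needed. There are two drawbacks. Final mechanism scores come later than real-time reads would. The reader may also recall a specimen already read in real time; coding from the outset reduces this but does not abolish it. Masking removes the part of the error due to expectation and leaves ordinary reading error in place.

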#### 14.6.2 Immunoelectron Microscopy / Production of Anchoring Fibrils

Biopsies collected for the purpose of IEM will be evaluated for the presence of anchoring fibrils, LH24 and mAb185 antibody staining and C7 expression. Evaluation of each item from each biopsy will be scored by a qualified reader. LH24 and mAb185 antibody staining and anchoring fibrils will be evaluated and considered to be present if a score of + is observed.

The percent of target wounds with a + score for each item evaluated will be reported at each post-treatment visit by treatment for each study phase. For quantitative analysis, the obtained results will be assigned a numeric value of 0 and 1, respectively, for – and +. Change in score from baseline will be evaluated and reported for each post-treatment visit by treatment and study phase and compared between treatments for each study phase. These analyses will be performed for both FAS and PP populations.

#### 14.6.3 Target Wound Area

Dimensions of target wounds (treated and control)/ partial wounds will be obtained using the Canfield VECTRA H1-270 System. Dimensions obtained will include length, width, and area (in cm^2). Change in area and other dimensions from baseline initial target wound identification and between visits will be evaluated.

The healed skin area of the target wounds (treated and control)/ partial wound will be evaluated using photographs by the investigator at each post-treatment visit and by treatment and study phase, and will be compared between treatments for each study phase.

The percent of change in the target wound (treated and control) / partial wound area from baseline will be assessed by the investigator at each post-treatment visit and by treatment and study phase, and will be compared between treatments for each study phase.

The proportion of target wounds (treated and control) / partial wounds achieving complete wound closure (≥ 90%) will be reported at each post-treatment visit by treatment and study phase and compared between treatments for each study phase.

These analyses will be performed for both FAS and PP populations.

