# 3 Experimental Plan

### 3.1 Study Design

This is a Phase I/II Study of FCX-007 (Genetically-Modified Autologous Human Dermal Fibroblasts) for Recessive Dystrophic Epidermolysis Bullosa (RDEB) being conducted by Fibrocell to evaluate FCX-007 in subjects with RDEB. Up to twelve subjects will be enrolled, up to six (6) in Phase I, and up to six (6) in Phase II. Phase I will enroll adult subjects only; Phase II can enroll adults and pediatric subjects (aged seven (7) or older). Within Phase I, subjects will be assigned to one of two arms: subjects with NC1+ status will be enrolled into Arm A and subjects with NC1- status will be enrolled into Arm B. The arms will enroll independently. In Phase I, the study may enroll an equivalent number of subjects to Arm A and Arm B (n=3 each arm). In Phase II, the study will target enrolling 3 subjects to each arm, but will allow a disproportionate distribution of subjects between Arm A and Arm B to equal 6 total subjects.

Figure 2 - High-Level Study Design

One administration of FCX-007 will consist of up to sixty (60) 0.25 mL intradermal injections in wounded and/or intact skin. The majority of the injections will be administered around the margin of target wounds and at least 6 injections will be administered to intact skin. The Investigator will attempt to administer all 15mL of FCX-007. This will be accomplished by selecting target wounds that are as close as possible to 54 linear cm, leaving at least 6 administrations for intact skin, for a total of 60 injections.

For the wound administrations, subjects will receive FCX-007 administered intradermally to one, two or three paired target wounds at Visit 3 (Day 0). Subjects will receive a second administration to wounded and/or intact skin at Visit 5 (Week 4).

In this study, one wound in each target wound pair will be used as a control for efficacy and safety evaluations. FCX-007 administered wounds will be compared within paired target wounds to untreated wounds.

CONFIDENTIAL Page 17 of 75

Final Version 8.0, 29 Oct 2019

As there is no previous human experience with FCX-007, treatment administration will be staggered in two places:

- 1. Between the first and second enrolled subjects in each arm.
- 2. Between the third and fourth enrolled subjects in each arm.

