# 3.3 Number and Source of Subjects

The enrollment target is up to twelve (12) subjects: Up to six subjects in Phase I and up to six (6) subjects in Phase II. A seventh subject may be enrolled into Phase II at the discretion of the sponsor.

In Phase I, 3 NC1+ subjects may be enrolled to Arm A and 3 NC1- subjects may be enrolled to Arm B. In Phase II, the study will target enrolling 3 subjects to each arm, but will allow a disproportionate distribution of subjects between Arm A and Arm B to equal 6 total subjects. All potential subjects must be properly consented, meet all inclusion/exclusion criteria, and undergo all screening procedures to be eligible for participation in this study.

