## 14.1 Number of Subjects

A formal sample size calculation was not performed for this study. The sample size is based on what was considered an adequate number of subjects for a pilot study to obtain sufficient information on the safety and effectiveness of FCX-007.

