#### 14.2 General considerations

Data will be summarized by treatment regimen and, when applicable, by study visit. Descriptive statistics (number and percentage for categorical data, mean, median, range, standard deviation and N for continuous data) will be presented for each evaluable parameter for change from baseline as well as the value at each timepoint. For discrete variables, descriptive analyses will be based on numbers of subjects (or wounds) and related percentages.

All listings, summaries, figures, and statistical analyses will be generated using SAS version 9.1 or other validated software. When applicable, statistical comparisons between treatments will account for correlated and/or paired data since the data are comprised of multiple wounds on the same individual. Statistical analyses will be exploratory and performed using 2-sided tests at a Type I error rate of 0.05.

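### Treated and control wounds are compared only within each phase of six or seven subjects; a pooled, phase-stratified comparison should be added

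*Combined protocol and SAP*

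**What the plan says.** Section 14.6.1 says that the change in C7 score "will be compared between treatments for each study phase". Section 14.6.2 uses the same construction for anchoring fibrils and antibody staining. Section 14.6.3 uses it for healed area, percent change in area and the proportion of wounds closed, each "compared between treatments for each study phase". Nothing in section 14 describes a comparison over both phases together.

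On size, section 3.1 says "Up to twelve subjects will be enrolled, up to six (6) in Phase I, and up to six (6) in Phase II", and section 3.3 adds "A seventh subject may be enrolled into Phase II at the discretion of the sponsor". Section 14.1 says "A formal sample size calculation was not performed for this study" and calls the study a pilot. Section 14.2 says "Statistical analyses will be exploratory and performed using 2-sided tests at a Type I error rate of 0.05" and asks that comparisons allow for correlated or paired wounds, but names no test or model. Section 14.9 plans no imputation for efficacy.

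The secondary efficacy objective in section 2.2.2 is a single intra-subject paired comparison of treated with untreated wounds, with no reference to phase. Sections 3.1 and 9 describe one product, administrations at Day 0 and Week 4, and an untreated paired control, with no difference between phases. The stated difference is age: adults in Phase I, adults and children from seven in Phase II.

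**The concern.** The objective asks one question, but the analysis answers it twice, each time with about half of the subjects, and the plan gives no reason for the split. The boundary between the phases is a safety gate: under section 11.1.2 the DSMB decides whether adults continue and whether children may enter. It does not change the treatment or the control. Each subject supplies both the treated and the control wound, so a difference in age mix between phases cannot confound the within-pair contrast, although it may modify the effect.

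What is at stake is precision. Section 14.1 justifies the sample size by the information it should give on safety and effectiveness. Reading the comparisons only phase by phase uses the efficacy and mechanism data of a rare-disease sample inefficiently. If pooling is decided only after the by-phase results are known, it becomes a post hoc choice.

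**Working it through.** The plan states no effect size, SD or power, so there is no figure to reproduce. The effect sizes below are assumptions for illustration.

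**Inputs from the protocol:** two-sided 0.05 (14.2); 6 subjects per phase, or 7 in Phase II (3.1, 3.3), hence 12 or 13 in total; one to three wound pairs per subject (3.1); no imputation (14.9).

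**1. Precision, whatever the test.** For a mean within-pair difference with one pair per subject, the standard error is SD/√n. Going from n=6 to n=12 divides it by √(12/6) = 1.41, so one phase holds half of the information. The 95% half-width is t(0.975, df) × SD/√n:

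- n=6, df 5: 1.05 SD
- n=12, df 10 (one degree of freedom spent on phase): 0.64 SD

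**2. Paired t-test power, assumed mean difference 1 SD** (noncentral t, noncentrality √n):

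| n | power |
|---|---|
| 6 | 51% |
| 7 | 60% |
| 12 | 88% |
| 13 | 91% |

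Stratifying by phase at n=12 (df 10) gives 87.6% instead of 88.3%, so stratification costs almost nothing.

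**3. Smallest attainable p for a subject-level exact sign or McNemar test:** 2 × 0.5^n, with n the number of untied (discordant) subjects.

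- n=4: 0.125
- n=5: 0.0625
- n=6: 0.031; with one subject against, 2 × (6+1)/64 = 0.219
- n=7: 0.016; with one subject against, 2 × (7+1)/128 = 0.125
- n=12: 10 of 12 is enough, 2 × (66+12+1)/4096 = 0.039

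So 0.05 is out of reach with five or fewer informative subjects. At six or seven it is reached only if no untied subject goes the other way. In a phase of six, one tie or missed visit leaves five. The signed-rank test has the same floor but at n=7 tolerates one small opposite result (W ≤ 2, p = 0.047).

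**4. Exact McNemar power for closure, one pair per subject, wounds in a pair assumed independent.** The probability that only the treated wound closes is b = p_T(1 − p_C); that only the control closes, c = p_C(1 − p_T). At n=6 power is b^6 + c^6.

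- 70% vs 20%: b = 0.7 × 0.8 = 0.56, c = 0.2 × 0.3 = 0.06; power 0.56^6 + 0.06^6 = 3%
- 80% vs 10%: b = 0.8 × 0.9 = 0.72, c = 0.1 × 0.2 = 0.02; power 0.72^6 + 0.02^6 = 14%

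Summing over discordant counts in the same way gives, for n=7 and n=12, 10% and 50% (70 vs 20), and 35% and 90% (80 vs 10).

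**5. Do extra pairs remove the limit?** For wound area and healing, partly. With two pairs in each of six subjects, a pair-level randomisation test has a floor of 2 × 0.5^12 = 0.0005. For the mechanism endpoints they help less: Table 2 schedules one wound biopsy per assay per visit, and section 10.1.1 lets the biopsied target wound vary between visits.

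**The case against.** The strongest reply is that the plan names no exact subject-level test, so the floor in step 3 is a benchmark brought in from outside. Section 14.2 foresees several wounds per subject and allows for their correlation; a mixed model, a paired t-test or a pair-level randomisation test is not bound by that floor. This stands. A reader might infer that the by-phase tests cannot work at 0.05. The documents do not support that: it holds only for sign or rank tests with five or fewer informative subjects, and at six or seven even those tests can reach the level.

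A reader might also infer that a real effect would probably be reported as non-significant in both phases. That depends on the assumptions. With a paired t-test at 1 SD and six per phase, the chance is (1 − 0.507)² = 24%. With McNemar at 70% vs 20% it is (1 − 0.031)² = 94%. The plan fixes neither the test nor the effect.

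The remaining points also have force. Safety is the primary objective, the tests are exploratory, and no decision depends on a p-value: the move to Phase II rests on DSMB review and single-wound criteria for benefit (11.1.2). Phase II may include children. The summary of changes shows that the Phase II control, the number of injections and the timing of the second administration changed between versions, and the protocol does not say which subjects were treated under which version. Homogeneity across phases therefore cannot be shown from the documents. These points limit the severity and argue for stratifying by phase and keeping by-phase results. They do not argue for leaving out a pooled estimate.

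**Conclusion.** The point holds as a loss of information in exploratory comparisons. It is not the failure of a confirmatory test. All between-treatment comparisons in 14.6.1 to 14.6.3 are by phase and none is pooled, although the objective and the current design text do not distinguish the phases on treatment or control. The cost is about half of the information per comparison, or a standard error 1.41 times as large when the phases are equal in size.

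The halving assumes equal phases and similar within-pair variability. The power figures also assume one pair per subject and effect sizes that the protocol does not give. More pairs raise the absolute figures, and pooling still adds precision. The change is worth making but does not endanger the trial's primary purpose.

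**What to change.** In sections 14.6.1 to 14.6.3, add a pooled Phase I and II within-pair comparison as the main exploratory analysis for each endpoint, stratified by phase and with subject as the cluster. Name the test or model. Keep the by-phase results beside it.

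The cost is analysis-plan wording and one more table per endpoint; no visits, biopsies or subjects are added. The drawback is that the pooled estimate averages over adults and children, and over any subjects treated under earlier protocol versions with a different control or second-dose timing. A listing by protocol version, or a sensitivity analysis restricted to subjects treated under the same control and schedule, should therefore accompany it. The change should be fixed before the by-phase efficacy results are examined; if they have already been seen, the report should say so.

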#### 9.3.1 Investigator Assessment of Wound Healing

The investigator will assess wound healing of target wounds (treated and control/untreated) based on the digital images of the target wounds. The investigator will assess wound healing of target wounds from 0% to 100% healed on a categorical scale. The wound healing assessment will be captured in the following categories.

- 0%
- 1-9%
- 10-24%
- 25-49%
- 50-74%
- 75-89%
- 90-99%
- 100%

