#### 14.6.3.1 Investigator Assessment of Wound Healing

The investigator will assess wound healing of target wounds (treated and control/untreated) based on the digital images of the target wounds. The investigator will assess wound healing of target wounds from 0% to 100% healed on a categorical scale. The wound healing assessment will be captured in the following categories.

- 0%
- 1-9%
- 10-24%

CONFIDENTIAL Page 61 of 75

Fibrocell Technologies RDEB Phase I/II Protocol Final Version 8.0, 29 Oct 2019

- 25-49%
- 50-74%
- 75-89%
- 90-99%
- 100%

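### Section 14.6.3 counts wounds scored 90–99% healed as completely closed, and section 9.2 describes no concealed method for choosing the treated wound of a pair

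*Combined protocol and SAP*

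**What the plan says.** **Closure.** Section 14.6.3 plans that the proportion of treated and control wounds "achieving complete wound closure (≥ 90%) will be reported at each post-treatment visit by treatment and study phase", and compares it between treatments within each phase. Section 9.3.1 defines the score: "The investigator will assess wound healing of target wounds from 0% to 100% healed on a categorical scale". Sections 9.3.1 and 14.6.3.1 print the same eight categories: 0, 1–9, 10–24, 25–49, 50–74, 75–89, 90–99 and 100%.

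Section 14.6.3 draws on two kinds of data. Wound dimensions "will be obtained using the Canfield VECTRA H1-270 System", while healed area and percent change are assessed by the investigator. The sentence on closure does not say which supplies the 90%. Objective 2 in section 2.2.2 points to the investigator, "comparing FCX-007 treated wounds to untreated wounds through investigator assessment of wound healing based on the digital images of wounds".

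**Assignment.** Section 3.1 pairs wounds by similarity of area, and section 7.3.1 makes the final selection at Visit 2. Section 9.1.2 has the investigator plan without knowing which wound will be treated. Section 7.3.2 puts random assignment at Visit 3 only. Section 9.2 has the investigator label the wounds A and B and then assign them at random. No section names a sequence, a system, an independent holder or a concealment step.

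**Status.** Section 14.2: "Statistical analyses will be exploratory and performed using 2-sided tests at a Type I error rate of 0.05". Section 14.1: "A formal sample size calculation was not performed for this study".

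**The concern.** The word complete conflicts with the plan's own scale, which has a separate category just below full healing. A table row named complete wound closure could include wounds that the investigator judged not fully healed. A report or abstract may carry the name without the cut-off.

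The second issue is independent of the first. Area is the only factor named for matching within a pair, so two paired wounds may differ in other ways. Once a pair is fixed, chance alone should decide which wound is treated. If the investigator makes that choice with no described method, the report cannot document that it did. The same role then scores both wounds, one of them an untreated control, and no masking is stated.

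**Working it through.** The plan states no sample size, power or closure rate, so there is no figure of its own to reproduce.

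**Step 1: map the cut-off onto the scale.** Categories meeting ≥90% are 90–99% and 100%. The only category meeting 100% is 100%. The cut-off falls on a category boundary, so the endpoint can be computed. The fault is in its name and its unstated source.

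**Step 2: try the other source.** If measured area supplies the value, a 90% reduction leaves 100 − 90 = 10% of the baseline area. A wound with up to 10% of its baseline area open would count as completely closed. The label overstates on either reading.

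**Step 3: size of one wound.** Inputs are up to six subjects per phase, an optional seventh in Phase II (section 3.3), and one to three pairs per subject (section 3.1). Each pair gives one wound per group, so n = subjects × pairs per subject. The shift in a group's proportion is k/n, where k is the number of its wounds scored 90–99%.

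| Subjects | Pairs each | n per group | k = 1 | k = 2 |
|---|---|---|---|---|
| 6 | 1 | 6 | 16.7 points | 33.3 points |
| 6 | 2 | 12 | 8.3 | 16.7 |
| 6 | 3 | 18 | 5.6 | 11.1 |
| 7 | 1 | 7 | 14.3 | 28.6 |
| 7 | 2 | 14 | 7.1 | 14.3 |
| 7 | 3 | 21 | 4.8 | 9.5 |

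**Step 4: effect on the comparison.** Change in the treated–control difference = (k treated − k control)/n. This is zero when the two counts are equal. Otherwise each excess wound moves the difference by 1/n, toward FCX-007 or toward control.

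**Step 5: effect on a test, for scale only.** Treat pairs as independent, although section 14.2 says correlation will be accounted for where applicable. In an exact two-sided sign test, five discordant pairs all in one direction give p = 2 × 0.5⁵ = 0.0625. Six give p = 2 × 0.5⁶ = 0.031. Moving one wound between 90–99% and 100% can therefore carry a per-phase result across 0.05.

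**Step 6: assignment text, read together.** Sections 7.3.1, 7.3.2 and 9.1.2 limit foreknowledge while pairs are chosen. They say nothing about how the choice within a fixed, labelled pair is generated or concealed. Section 9.2 gives that step to the investigator and adds only that it is random. No bias can be calculated from this.

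**The case against.** The case for leaving the text alone has five parts.

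- **The threshold is visible.** It is printed beside the term and applies equally to both groups. Section 14.2 plans "number and percentage for categorical data", so the 90–99% and 100% counts should be tabulated anyway. This stands, and it means that no data are lost. It does not correct the named endpoint, which is the one compared between treatments.
- **The source is fairly clear.** The two paragraphs before the closure sentence name the investigator, objective 2 does too, and 90% is a boundary of the investigator's scale. This largely stands: the investigator score is the likely source, but the sentence should say so. If it is the source, the conflict with the scale is direct.
- **The arithmetic only shows that small samples are coarse.** It is indeed 1/n and 2/n, and it assumes full enrolment and equal numbers of pairs per subject. It is a scale and not a bound. Fewer subjects, or wounds not assessed when Visit 7 or 9 is held by telephone, make each step larger.
- **Assignment is already protected in part.** Three sections call it random, pairs are fixed first, and both wounds enter the study whichever is treated. Section 9.1.1 also requires clean, uninfected, well-vascularized wounds, and section 9.1 favors stable areas. These points narrow differences within a pair. They do not show how the treated wound is chosen.
- **The two points are unrelated and the analyses exploratory.** Both statements are correct. The closure arithmetic lends no weight to the assignment point, and neither touches the primary objective of safety.

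**Conclusion.** Both points hold and should be corrected.

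The closure label is wrong as written. Following section 14.6.3 with the investigator score counts wounds scored as not fully healed as completely closed. In a full phase of six subjects, each such wound is worth 5.6 to 16.7 points in its group's proportion, or 4.8 to 14.3 points with seven subjects. This assumes every subject contributes the same number of pairs and every wound is assessed. How many wounds will be scored 90–99% is unknown, so no total and no direction for the treated–control difference is claimed.

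The assignment point is closer to missing detail. The plan states that assignment is random but gives no means of documenting or concealing it. No bias is claimed or computable.

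The consequence is limited to exploratory secondary analyses in a pilot, which also plans measured wound area and biopsy results.

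**What to change.** 1. **Section 14.6.3.** Define complete wound closure as the 100% category of the investigator score in section 9.3.1. Report ≥90% healed (90–99% plus 100%) as a separate row under that name, and compare both rows between treatments in the way already planned. Cost: wording, one extra table row and one extra exploratory comparison per visit and phase. The headline closure proportion will fall if any wounds are scored 90–99%.
2. **Section 9.2.** For subjects not yet assigned, replace assignment by the investigator with a random list for wounds A and B. The sponsor prepares it, conceals it by subject and pair, and has it opened at Visit 3 after pre-dose imaging, the visit where section 7.3.2 already lists assignment. Cost: one entry per pair, so 12 × 1 = 12 to 12 × 3 = 36 entries, or 13 × 1 = 13 to 13 × 3 = 39 with the optional extra subject, and fewer if some are already assigned. It cannot help those already assigned. If there are any, the report should state which method applied to whom.

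Neither change needs a new visit, image or reader. Neither removes the unmasked scoring by the investigator, which remains a limitation of the comparison.
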